13.1.8 Other Considerations

Toxicity, patterns of treatment failure observed in this study and scientific discoveries or changes in standard care will be taken into account in any decision to terminate these trials earlier than anticipated.

13.2 Evaluation of ESR1 alterations and markers of endocrine resistance in patients treated with either tamoxifen or Z-Endoxifen HCl (Alliance A011203-ST1)

13.2.1 Objectives

- 13.2.1.1** To examine whether DNA alterations as measured by Foundation medicine in all coding exons of 287 cancer-related genes as well as 78 polymorphisms in 34 ADME-related genes (assessed using a biopsy of metastatic disease obtained after progression on AI) are associated with longer PFS or higher response rates in the Z-Endoxifen HCl arm compared to the tamoxifen arm.
- 13.2.1.2** To examine whether SRC3 (AIB1) IHC expression levels (assessed using a biopsy of metastatic disease obtained after progression on AI) is associated with longer PFS or higher response rates in the Z-Endoxifen HCl compared to tamoxifen arm.

13.2.2 Analysis methods – DNA alterations

Data will be returned from Foundation Medicine as presence or absence of various DNA alterations, along with description of type and location of the alteration. The nature of alterations found in each pathway and gene will be described in tabular format. Association of presence or absence of DNA alterations with PFS will be assessed overall (presence/absence of any alteration), by pathway (presence/absence of alterations within a given pathway), and by gene (presence/absence of alterations within a given gene) via Cox regression with the goal of evaluating hazard ratio estimates and confidence intervals. Similarly, associations with response rates will be evaluated via logistic regression overall, by pathway, and by gene with the goal of evaluating odds ratio estimates and confidence intervals. Alterations will be considered together (polymorphisms, mutations, amplifications, indels, and fusions combined) as well as by type of alteration, e.g., for polymorphisms alone, mutations alone, etc. Model fit and stability will be evaluated, and exact methods used if needed. Due to sample size and expected prevalence rates, we expect the ability to adjust for covariates to be limited. These analyses will be performed in data from both treatment arms combined, as well as within treatment arm. This allows us to assess both prognostic and predictive ability in an exploratory fashion. The ER and PI3K pathways are of primary interest; other pathways will be examined as well. In addition, raw data will be received, and state-of-the-art bioinformatics algorithms utilized to assess the potential for genetic alterations not yet discovered.

13.2.3 Power – DNA alterations

The total trial sample size is 80 patients, with 40 for each treatment. Previous experience demonstrates successful assay rates range from 73% in ER+ Her2- patients [44] to 95% successful assay rate in a diverse set of cancers [45]. Based on these rates, the expected sample size per treatment arm is from 29 to 38. A previous study in this patient population found 96% of subjects to have at least one known somatic alteration, and 104 genes to have at least one known somatic alteration [44]. The same study found 56% of patients to have genetic alterations in the PI3K pathway and 44% to be wild type. Given the sample size and expected prevalence rates, these analyses are considered to be exploratory and hypothesis generating.

13.2.4 Analysis methods – SRC3 (AIB1) and PKC β 1 IHC expression levels

Approximately 25% of patients are anticipated to have metastatic SRC3-positive disease. Within each treatment arm, a point and interval estimate of the difference in tumor response rate between those with metastatic SRC3-positive disease and those with metastatic SRC3-negative disease will be constructed using the properties of the binomial distribution. Also, a point and interval estimate of the odds of disease progression among those with metastatic SRC3-positive disease relative to those with metastatic SRC3-negative disease will be ascertained from the parameter estimates of fitting a proportional hazard model to the progression data. The proportion of patients with metastatic PKC β 1 expressing breast cancer is unknown. Within each treatment arm, a point and interval estimate of the difference in tumor response rate between those with metastatic PKC β 1-positive disease and those with metastatic PKC β 1-negative disease will be constructed using the properties of the binomial distribution. Also, a point and interval estimate of the odds of disease progression among those with metastatic PKC β 1-positive disease relative to those with metastatic PKC β 1-negative disease will be ascertained from the parameter estimates of fitting a proportional hazard model to the progression data.

13.3 DNA alterations in patients treated with either tamoxifen or Z-Endoxifen HCl (Alliance A011203-ST2)

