14.1.2 Objectives

- 14.1.2.1 To examine whether *ESR1* alterations (defined as either ER activating mutations or ER amplification) (assessed using a biopsy of metastatic disease obtained after progression on AI) is associated with longer PFS or higher response rates in the Z-Endoxifen HCl arm compared to the tamoxifen arm.
- 14.1.2.2 To examine whether SRC3 (AIB1) or PKC β 1 IHC expression levels (assessed using a biopsy of metastatic disease obtained after progression on AI) is associated with longer PFS or higher response rates in the Z-Endoxifen HCl compared to tamoxifen arm.
- 14.1.2.3 To examine whether ER α alterations (defined as either ER activating mutations or ER amplification) are associated with longer PFS or higher response rates in the Z-Endoxifen HCl arm compared to the tamoxifen arm.

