14.1.3 Methods

Patients are eligible for A011203 if their tumor is determined to be ER α positive. An additional 2-3 research cores will be obtained for the tissue translational studies for consenting patients. A biopsy of metastatic disease for patients that have progressed on prior hormonal therapy may be considered a standard of care, since multiple studies have demonstrated that ER and HER2 expression can change, and this change is associated with differences in DFS and OS [48]. Specifically, tamoxifen is not indicated for ER negative breast cancer. Furthermore, if the tumor is determined to be HER2+, patients would be eligible for anti-HER2 based therapy off study. Therefore, a biopsy at the time of pre-registration is required for all patients for confirmation of ER status. See Section

[6.2.3](#) for details of specimen collection.

A portion of the tissue, corresponding to approximately 75% of the total from the biopsy as described in Section [6.2.3](#) will be fixed in formalin and sent to the Alliance Biorepository at Ohio State University for these analyses. There, the tumor block (s) will be used for nucleic acid extraction for the following translational objectives: DNA (Foundation medicine) and RNA (SET index) as well as sections cut for IHC analyses of PKC β 1 and SRC3.

There, either one or two cores (depending on total volume) will be cut for an H&E (to confirm tumor) followed by 10 unstained sections (10 micron) for DNA (Foundation Medicine) and RNA extraction (SET index). Three 5 micron sections will additionally be cut for assessment of PKC β 1 [49] as well as total and phosphorylated SRC3 using the method previously described [50]. The Foundation Medicine DNA sequencing assay will be performed as previously described [37]. For the SET index, random primer reverse transcription will be performed using the Sensation Plus kit (Affymetrix) and labeled cDNA will be hybridized to Affymetrix U133 gene expression arrays. The SET index will be calculated from the normalized gene expression values using pre-defined methods. SET index will be compared to PFS between and across treatments as a continuous variable and as pre-defined categories of low and high SET index.

The remaining tissue any residual DNA/RNA will be stored in the Alliance Biorepository at Ohio State University. See [Section 6.2.3](#) for shipping instructions.

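### Section 13.2.4 analyses SRC3 and PKCβ1 IHC only as positive versus negative, although the objectives ask about expression levels; adding the score to the Cox model for PFS costs little

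*Combined protocol and SAP*

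**What the plan says.** The objective in 13.2.1.2 begins "To examine whether SRC3 (AIB1) IHC expression levels" and names SRC3 only. The matching objective in 14.1.2.2 covers SRC3 or PKCβ1 and asks whether "IHC expression levels (assessed using a biopsy of metastatic disease obtained after progression on AI) is associated with longer PFS or higher response rates" in one arm compared with the other.

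The analysis in 13.2.4 is binary throughout. Within each arm it gives a difference in response rate between marker-positive and marker-negative patients. For progression it gives "a point and interval estimate of the odds of disease progression among those with metastatic SRC3-positive disease relative to those with metastatic SRC3-negative disease", obtained by "fitting a proportional hazard model to the progression data", so the quantity is in effect a hazard ratio. PKCβ1 gets the same two estimates. No test is specified.

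On prevalence, 13.2.4 says: "Approximately 25% of patients are anticipated to have metastatic SRC3-positive disease". The proportion of patients with PKCβ1 "expressing breast cancer is unknown".

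Section 14.1.3 plans staining for PKCβ1 and for "total and phosphorylated SRC3 using the method previously described". The assays are given by citation, without a scale or threshold, and 13.2.4 does not say which SRC3 stain makes a tumour positive. The same section treats the third tissue marker differently: "SET index will be compared to PFS between and across treatments as a continuous variable and as pre-defined categories of low and high SET index".

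**The concern.** The question is about level and the analysis is about a binary call. If the hazard of progression changes gradually with expression, grouping everyone above a cut and everyone below it throws away the ordering within each group. That matters more when the groups are small and uneven, as they are expected to be for SRC3. The intervals that 13.2.4 exists to report would then be wider than the same stained sections allow. The SET index, measured on the same research block, is spared this because it is also analysed as a continuous variable.

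At stake is the precision of exploratory marker–PFS estimates. The treatment comparison is not touched.

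**Working it through.** **Sample size.** Section 13.2.4 gives no sample size or precision of its own. The nearest figure is in 13.2.3, for the DNA assay: 40 × 0.73 = 29.2 and 40 × 0.95 = 38.0, which reproduces the stated 29 to 38 per arm. I assume the same range for IHC.

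**Group sizes.** 0.25 × 29 = 7.25 and 0.25 × 38 = 9.5. Each arm therefore compares about 7 to 10 SRC3-positive patients with about 22 to 28 negative.

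**Precision of the planned estimate.** SE(log HR) ≈ 1/√[d·p(1−p)], with d events and p = 0.25, so p(1−p) = 0.1875.
- 29 patients, 90% with events (d = 26.1): SE = 0.452, and the 95% interval runs a factor exp(1.96 × 0.452) = 2.4 either side.
- 38 patients, all with events: SE = 0.375, factor 2.1.

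**Loss for a normal score.** With a log-linear effect and a large sample, the information kept by a cut at share p is φ(z_p)²/[p(1−p)]. At p = 0.25 this is 0.3178²/0.1875 = 0.539, a loss of 46%. On those assumptions, 29 to 38 patients analysed as positive/negative are worth about 16 to 20 analysed on the score. At 20% positive the loss is 51%, and at 30% it is 42%.

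**Other continuous shapes, cut at 25%, linear effect** (loss = 1 − squared correlation of the score with its indicator): exponential 36%, uniform 44%, t with 5 df 52%, lognormal 56%.

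**Small samples.** I simulated Cox score tests with a normal score, 10% censoring and log HR 0.2, 0.4 and 0.6 per SD (assumed). Information kept is the squared ratio of mean z-values; for example, at n = 36 and log HR 0.4, (1.716/2.071)² = 0.687.
- n = 36: loss 26–32%.
- n = 76: loss 35–37%.
- n = 2,000: loss 43%, 40% and 37% for the three effects.

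So 46% is the limit for small effects in large samples.

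**Four-level score (0 to 3), 25% at 2 or 3.** The frequencies are assumed.
- 0.25, 0.50, 0.15, 0.10: variance 2.0 − 1.1² = 0.79; covariance with the indicator 0.60 − 1.1 × 0.25 = 0.325; kept 0.325²/(0.79 × 0.1875) = 0.713; loss 29%.
- 0.75, 0, 0.15, 0.10: variance 1.5 − 0.6² = 1.14; covariance 0.60 − 0.6 × 0.25 = 0.45; kept 0.45²/(1.14 × 0.1875) = 0.947; loss 5%.

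**True step at the cut.** Nothing is lost.

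**PKCβ1.** The share is unknown, so the formula has no input. With an assumed normal score it would run from 36% at 50% positive to 66% at 10% or 90%, which is a range of assumptions and not an estimate.

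**The case against.** Much of the case on the other side stands.

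- The 46% rests on a normal, continuously scored marker with a log-linear effect. The documents state none of these. IHC may be read on a few levels, where the loss is smaller, and a genuine threshold effect would lose nothing.
- The SET index is a calculated continuous value, so its treatment does not prove that IHC can be handled identically. An ordered score is enough for the argument, however.
- A reader might infer that the PKCβ1 cut will be chosen after its distribution is seen. The documents do not show this. A threshold can be fixed without knowing how many patients exceed it, and the papers cited in 14.1.3 may contain scoring rules.
- A reader might extend the loss to response. No calculation supports that. A within-arm logistic model could also fail: section 1.3.4 cites a 0% objective response rate for tamoxifen alone after relapse on an AI. The planned binomial difference can still be estimated with few or no responders.
- The 29 to 38 per arm may be optimistic, since ST1 is optional (4.7.1) and inadequate research tissue is accepted (6.2.2).
- Stakes are low. SRC3 and PKCβ1 IHC are absent from the section 2.3 objectives, and 13.2.3 calls the DNA work in this sub-study exploratory.

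None of this removes the mismatch between objectives about level and an analysis that uses only a binary call.

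**Conclusion.** The point holds as a cheap improvement of low severity. The plan asks about expression levels and analyses only positive versus negative, without stating a scale, a cut-off or the SRC3 stain that counts.

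If the SRC3 effect on PFS is graded and about 25% are positive, the loss is up to about 46% of the information under a roughly normal score with a log-linear effect, nearer 26–32% at the size of one arm under the simulated effects. It is about 5–29% for a four-level score and zero for a step at the cut. Heavier-tailed or skewed scores can exceed 46%, so that figure is not a general ceiling.

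It would be tempting to read this as a flat 46% loss for both markers. The documents do not support that: the 25% is for SRC3 alone, and no figure can be given for PKCβ1. The primary endpoint is unaffected.

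**What to change.** In 13.2.4:

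- Record the IHC score for each stain as well as the positive/negative call.
- Add, within each arm, a Cox model for PFS with the score as an ordered or continuous variable, in line with 14.1.3 for the SET index.
- State whether total or phosphorylated SRC3 defines positivity.
- Fix the scoring scale and cut-off for both markers in writing before outcomes are linked. Section 6.2.3 has the blocks sectioned at the end of the study, so there is time to do this.
- Keep the planned positive/negative estimates, including the binomial response-rate difference. They also help to show a threshold effect.
- Model response on the score only if there are enough responders, with exact or penalised methods if they are sparse. Section 13.2.2 already allows exact methods for the DNA markers.

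The cost is wording and one extra recorded field, with no new tissue, staining or patients. The downsides are a log-linearity assumption and a few more exploratory models: three stains by two arms makes six Cox fits, which should be reported as exploratory.

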13.3.1 Objectives

- 13.3.1.1 To assess whether the molecular characteristics identified in the tumor biopsies are detectable in CTCs and/or cfDNA.
- 13.3.1.2 For each treatment arm, to examine ESR1 mutations or amplifications identified in CTCs or cfDNA change over time and explore the impact of these changes on PFS and response rates.

13.3.2 Analysis methods

For each patient, the genetic alterations seen in their tumor biopsy and their circulating tumor cells will be compared to ascertain which genetic alteration was seen in both tumor biopsy materials and CTCs, seen in only their tumor biopsy material, or seen in only their CTCs. For each alteration observed, we will tabulate the proportion of patients who had the genetic alteration seen in both tumor biopsy materials and CTCs, the proportion of patients who had the genetic alteration seen in only their tumor biopsy material, the proportion of patients who had the genetic alteration seen in only their CTCs, and the proportion of patients who did not have the genetic alteration in tumor biopsy materials or CTCs.

Toy et al. conducted a genetic analysis of tumors taken from individuals with metastatic ER-positive breast cancer whose tumors had grown or spread to new sites after at least 3 months with hormonal therapy. They found in 14 (17.5%) of 80 cases there were mutations in *ESR1* affecting the ligand-binding domain. The prevalence of mutations in this gene among the tumors from the patients who relapsed on hormonal treatment was higher than that seen in The Cancer Genome Atlas (TCGA) invasive primary (untreated) breast cancer and luminal A and luminal B primary breast cancer cases, suggesting that these mutations may have a role in the development of acquired resistance to hormonal treatment.

For each treatment arm:

- a point and interval estimate of the proportion of patients with *ESR1* mutated CTCs prior to the start of treatment or is found to have *ESR1* mutated CTCs during treatment at or prior to progression will be determined using the properties of the binomial distribution
- a point and interval estimate of the proportion of patients with *ESR1* mutated CTCs prior to the start of treatment who progress within the first 4 months of treatment will be determined using the properties of the binomial distribution
- a point and interval estimate of the hazard of disease progression among the patients with *ESR1* mutated CTCs prior to the start of treatment or at end of the second cycle of treatment relative to patients who do not have *ESR1* mutated CTCs either prior to the start of treatment or at end of the second cycle of treatment will be constructed using the results of fitting a Cox model to time to progression data.

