2.3 Correlative Science Objectives

- 2.3.1 To examine whether ER α alterations (defined as either ER activating mutations or ER amplification) are associated with longer PFS or higher response rates in the Z-Endoxifen HCl arm compared to the tamoxifen arm.
- 2.3.2 To determine changes in lipid profiles comparing tamoxifen and Z-endoxifen HCl.
- 2.3.3 For each treatment, to evaluate changes in markers of bone formation and absorption after 12 weeks (4 cycles) of treatment.
- 2.3.4 For all patients and by treatment arm, to determine whether progression-free survival differs with respect to the sensitive to endocrine therapy (SET) index.
- 2.3.5 To examine whether DNA alterations as measured by Foundation medicine in all coding exons of 287 cancer-related genes as well as 78 polymorphisms in 34 ADME-related genes are associated with longer PFS or higher response rates in the Z-Endoxifen HCl arm compared to the tamoxifen arm.
- 2.3.6 To assess whether the molecular characteristics identified in the tumor biopsies are detectable in the CTCs and/or cfDNA.
- 2.3.7 For each treatment arm: to examine changes in ER expression on CTCs, changes in ESR mutations or amplification in CTCs or CfDNA and explore the impact of these changes on PFS and response rates.

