14.2.2 Objectives

- 14.2.2.1** To assess whether the molecular characteristics identified in the tumor biopsies are detectable in CTCs and/or cfDNA.
- 14.2.2.2** For each treatment arm, to examine whether ESR1 mutations or amplifications identified in CTCs or cfDNA change over time and explore the impact of these changes on PFS and response rates.

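### The ST2 estimates in 13.3.2 pool baseline with on-treatment ESR1 positivity, so none reports acquired, persistent or cleared mutation or relates change to outcome, which is the stated objective

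*Combined protocol and SAP*

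**What the plan says.** Section 2.3 (objective 2.3.7) asks, for each arm, about "changes in ESR mutations or amplification in CTCs or CfDNA and explore the impact of these changes on PFS and response rates". Section 13.3.1 (13.3.1.2) asks how ESR1 alterations "identified in CTCs or cfDNA change over time and explore the impact of these changes on PFS and response rates", and 14.2.2.2 repeats this. The background in 14.2.1 likewise presents serial change and its correlation with patient outcome as the purpose of the blood sampling.

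Section 13.3.2 then lists three estimates per arm:

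- First: one proportion that counts a patient if she has ESR1 "mutated CTCs prior to the start of treatment or is found to have" them later; the later part covers every on-treatment sample, including the one at progression. A plain binomial interval is attached.
- Second: the proportion with ESR1 "mutated CTCs prior to the start of treatment who progress within the first 4 months of treatment".
- Third: a Cox hazard ratio by ESR1 status, for those with "mutated CTCs prior to the start of treatment or at end of the second cycle of treatment relative to patients who do not have" them at either time.

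The remaining analysis in 13.3.2 tabulates biopsy against CTC findings. That serves the concordance objective (13.3.1.1), not change.

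Under 6.2.4, CTC samples are taken at baseline, end of cycle 2, end of cycle 8 and progression.

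**The concern.** The objective is about change, but the first and third estimates are unions over time and the second looks only at baseline. In a union, a patient who loses her mutation, one who keeps it and one who gains it all count as positive. Section 13.3.2 motivates the analysis by a possible role of these mutations in acquired resistance, yet acquisition has no line of its own. Nothing relates a change in status to PFS or to response.

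Followed exactly, the plan would leave the second ST2 objective without a direct answer, although the samples needed for one are collected. A lesser issue is that the ever-positive proportion depends on how many samples a patient gives, which depends on how long she stays progression-free.

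**Working it through.** Section 13.3.2 gives no expected value, sample size or power for these estimates, so there is no planned figure to reproduce. The one prevalence it cites checks: 14/80 = 17.5%. That figure comes from tumour tissue in an outside series, not from CTCs in this trial.

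**What the estimates can and cannot show.** Take 40 patients in an arm (the design maximum, since ST2 is optional) and a pooled first estimate of 10/40 = 25%. Three different histories give it:

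| Positive at baseline | Newly positive | Acquired among baseline-negative | Exact 95% CI |
|---|---|---|---|
| 10 | 0 | 0/30 = 0% | 0 to 11.6% |
| 7 | 3 | 3/33 = 9.1% | 1.9 to 24.3% |
| 2 | 8 | 8/38 = 21.1% | 9.6 to 37.3% |

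If the second estimate is reported with the baseline-positive patients as its denominator, that denominator (10, 7 or 2) identifies the row: newly positive = 10 minus baseline-positive. Clearance stays hidden. In the middle row, anywhere from 0 to 7 of the 7 baseline-positive patients could have cleared by end of cycle 2, and all three estimates would still place every patient in the same group.

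**Dependence on sample count.** Inputs: 21-day cycles (section 5.1), so end of cycle 2 is day 42 = 1.38 months and end of cycle 8 is day 168 = 5.52 months; design medians of 3.0 and 6.0 months (13.1.3). Assume exponential PFS, S(t) = 2^(−t/median), and follow-up to progression. A patient then gives 2 samples if she progresses by day 42, 3 if between days 42 and 168, and 4 if later.

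- Tamoxifen: S(1.38) = 0.727 and S(5.52) = 0.279, so 27%, 45% and 28% give 2, 3 and 4 samples (mean 3.0).
- Z-Endoxifen: S(1.38) = 0.853 and S(5.52) = 0.529, so 15%, 32% and 53% (mean 3.4).

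The documents give no per-sample sensitivity or emergence rate, so a range is assumed, with 17.5% as the starting prevalence. With k samples:

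- no true change, sensitivity s: ever-positive = 0.175 × (1 − (1 − s)^k);
- perfect detection, emergence e per post-baseline sample: ever-positive = 1 − 0.825 × (1 − e)^(k−1).

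| Assumption | k = 2 | k = 3 | k = 4 | Tamoxifen | Z-Endoxifen | Difference (points) |
|---|---|---|---|---|---|---|
| No change, s = 0.3 | 8.9% | 11.5% | 13.3% | 11.3% | 12.1% | 0.8 |
| No change, s = 0.5 | 13.1% | 15.3% | 16.4% | 15.0% | 15.6% | 0.6 |
| No change, s = 1.0 | 17.5% | 17.5% | 17.5% | 17.5% | 17.5% | 0 |
| e = 5% | 21.6% | 25.5% | 29.3% | 25.5% | 26.9% | 1.4 |
| e = 10% | 25.75% | 33.2% | 39.9% | 33.0% | 35.6% | 2.6 |

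For scale, the 95% half-width of a proportion near 25% with n = 40 is 1.96 × √(0.25 × 0.75 / 40) = 13 points.

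**The case against.** The strongest reply has four parts.

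- *Acquisition is recoverable.* On its natural reading, the second estimate has the baseline-positive patients as its denominator, and subtraction from the first estimate's numerator gives the newly positive count. This stands, so a reader should not infer that the plan makes baseline and acquired mutation indistinguishable. The subtraction fails if the second estimate is taken over all patients. Even when it works, it gives a count over all later samples rather than at a fixed time, and it says nothing about clearance.
- *Unequal sampling does little.* A reader might infer that the arm with longer PFS will look appreciably more mutated through extra sampling alone. The documents do not support that. Patients are also sampled at progression; if mutations persist once acquired and are detected, that sample captures them and intermediate ones add nothing. Emergence over longer follow-up is a real cumulative frequency, not an artefact, and the emergence rows above do not separate the two. The differences are small against a half-width of 13 points, and 13.3.2 plans no between-arm contrast.
- *The stakes are low.* This is one of two objectives in an optional sub-study, worded as exploratory, with no test or power claim. That stands. Section 13.4, also correlative, nevertheless defines change from pre-treatment after two cycles, and ST2 has samples at the same two times.
- *Analysts could tabulate by timepoint anyway.* They could; the plan does not forbid it, but it does not ask for it either.

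**Conclusion.** The mismatch between objective and analysis holds on the text and needs no numerical assumption. No estimate in 13.3.2 reports acquired, persistent or cleared ESR1 mutation or relates change to PFS or response. Acquisition is at best derivable by subtraction; clearance cannot be seen.

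The dependence on sample count is secondary. The ever-positive proportion cannot fall as samples are added, but it stays flat with perfect detection and no emergence. The arm effect is about 0 to 3 points, assuming exponential PFS at the design medians, the tissue prevalence applied to CTCs, and the detection and emergence ranges shown.

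This is a minor, worthwhile improvement to a correlative sub-study. Nothing here touches the primary or secondary clinical analyses.

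**What to change.** Replace the first estimate, per arm, with exact intervals and the number sampled, by:

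- (a) baseline prevalence;
- (b) acquired: mutation at end of cycle 2 among baseline-negative patients sampled then;
- (c) cleared: no mutation at end of cycle 2 among baseline-positive patients sampled then.

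Report the same quantities separately for the end-of-cycle-8 and progression samples. The progression sample matters most for the acquired-resistance rationale.

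In the third estimate, replace the pooled group with change status at end of cycle 2 (acquired, persistent, cleared, never). Relate it descriptively to response and to PFS counted from that landmark, because the status is not known before then.

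The cost is wording and a small table; every sample is already planned. The downside is small cells. If 17.5% applied to CTCs, (c) would rest on about 0.175 × 40 = 7 patients per arm, fewer with opt-outs, and an observed 0/7 would have an exact upper 95% limit of 1 − 0.025^(1/7) = 41%. The landmark analysis also leaves out patients who progress by day 42, about 27% and 15% of the two arms under the design medians; their progression samples still appear in the separate table. Both are acceptable in an exploratory sub-study if the denominators are shown.
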